Appendix A

#	SAVOR-TIMI 53 trial definitions	Implementation in routine care	References/Rationale	Color coding
			
Please see the following Google Drive for further details or any missing information: https://drive.google.com/open?id=1WD618wrywYjEaXzflTcUK-VCcnb6b-gV
	Criteria
	Trial details- Negative trial		ICD-10 codes are not listed in this document because of excel cell size limitations and excessive number of ICD-10 codes. Full ICD-10 code lists will be available in the above Google Drive Folder (link above). ICD-9 to ICD-10 code conversions were completed using a SAS macro that implements forward/ backward mapping based on the CMS ICD-9 to ICD-10 mapping: https://www.ncbi.nlm.nih.gov/pmc/articles/PMC3037730/	Adequate mapping in claims
	EXPOSURE vs. COMPARISON			Intermediate mapping in claims
	Saxagliptin 5 mg QD (2.5 mg in subjects with moderate/severe renal impairment) vs placebo	Saxagliptin vs. 2nd generation sulfonylurea		Poor mapping or cannot be measured in claims
	PRIMARY OUTCOME			
	Composite of cardiovascular death, nonfatal myocardial infarction, or nonfatal ischemic stroke HR = 1.00 (95% CI 0.89-1.12)	
Measured 1 days after drug initiation in diagnosis position specified below and inpatient care setting:
 
Inpatient mortality/MI/Stroke --
 
For MI Any diagnosis position in inpatient care setting ICD-9 Dx 410.X (acute myocardial infarction) excluding 410.x2 (subsequent episode of care), as the principal (primary) or the next (secondary) diagnosis
 
For stroke Primary diagnosis position in inpatient care setting ICD-9 discharge diagnosis: 430.xx Subarachnoid hemorrhage (SAH) 431.xx Intracerebral hemorrhage (ICH) 433.x1 Occlusion and stenosis of precerebral arteries with cerebral infarction 434.xx (excluding 434.x0) Occlusion and stenosis of cerebral arteries with cerebral infarction 436.x Acute, but ill-defined cerebrovascular events
 
Mortality- See Mortality Sheet.
	
For MI:
 
►PPV 94% in Medicare claims data [Kiyota Y, Schneeweiss S, Glynn RJ, Cannuscio CC, Avorn J, Solomon DH. Accuracy of Medicare claims-based diagnosis of acute myocardial infarction: estimating positive predictive value on the basis of review of hospital records. American heart journal 2004;148:99-104.]
 
►PPV 88.4% in commercially-insured population [Wahl PM, Rodgers K, Schneeweiss S, et al. Validation of claims-based diagnostic and procedure codes for cardiovascular and gastrointestinal serious adverse events in a commercially-insured population. Pharmacoepidemiology and Drug Safety 2010;19:596-603.]
 
For stroke:
 
PPV of 85% or higher for ischemic stroke PPV ranging from 80% to 98% for hemorrhagic stroke
 
 
 
	Can't be measured in claims but not important for the analysis
	INCLUSION CRITERIA			
1	Diagnosed with T2DM based on the current American Diabetes Association guidelines	Patients with a diagnosis of T2DM (ICD-9 Dx code of 250.x0 or 250.x2) in the 180 days prior to drug initiation in any diagnosis position and inpatient or outpatient care setting .	Patorno, Elisabetta et al. "Cardiovascular outcomes associated with canagliflozin versus other non-gliflozin antidiabetic drugs: population based cohort study." BMJ 2018;360:k119 http://dx.doi.org/10.1136/bmj.k119	
2	Age ≥40 years	Age ≥40 years at drug initiation	Patorno, Elisabetta et al. "Empagliflozin and the Risk of Heart Failure Hospitalization in Routine Clinical Care: A First Analysis from the Empagliflozin Comparative Effectiveness and Safety (EMPRISE) Study." Circulation. 2019 Apr 8. doi: 10.1161/CIRCULATIONAHA.118.039177	
3	Glycated hemoglobin level of ≥6.5% (based on the last measured and documented laboratory measurement in the previous 6 months)	N/A		
4	High risk for a CV event defined as having either established CV disease and/or	-		
	• History of established cardiovascular disease -Ischemic heart disease, and/or	Measured 180 days prior to drug initiation in any diagnosis position and inpatient or outpatient care setting - Ischemic heart disease 410.xx-414.xx	Patorno, Elisabetta et al. "Cardiovascular outcomes associated with canagliflozin versus other non-gliflozin antidiabetic drugs: population based cohort study." BMJ 2018;360:k119 http://dx.doi.org/10.1136/bmj.k119	
			Patorno, Elisabetta et al. "Empagliflozin and the Risk of Heart Failure Hospitalization in Routine Clinical Care: A First Analysis from the Empagliflozin Comparative Effectiveness and Safety (EMPRISE) Study." Circulation. 2019 Apr 8. doi: 10.1161/CIRCULATIONAHA.118.039177	

Appendix A

4a
 
 - Peripheral vascular disease (eg, intermittent claudication), and/or - Ischemic stroke • Multiple risk factors for vascular disease - At least 55 years of age (men) or 60 years of age (women), AND at least one of the following additional risk factors 	
Measured 180 days prior to drug initiation in any diagnosis position and inpatient or outpatient care setting- Peripheral vascular disease (ICD9 diagnosis): 440.20 – 440.24, 440.29 – 440.32, 440.3, 440.4, 443.9
	
Patorno, Elisabetta et al. "Cardiovascular outcomes associated with canagliflozin versus other non-gliflozin antidiabetic drugs: population based cohort study." BMJ 2018;360:k119 http://dx.doi.org/10.1136/bmj.k119
 
Patorno, Elisabetta et al. "Empagliflozin and the Risk of Heart Failure Hospitalization in Routine Clinical Care: A First Analysis from the Empagliflozin Comparative Effectiveness and Safety (EMPRISE) Study." Circulation. 2019 Apr 8. doi: 10.1161/CIRCULATIONAHA.118.039177

 * Dyslipidemia (based on the last measured and documented laboratory measurement in the previous 6 months and defined as at least 1 of the following): 	
Measured 180 days prior to drug initiation in any diagnosis position and inpatient or outpatient care setting- Hyperlipidemia 272.0x-272.4x
	
Patorno, Elisabetta et al. "Cardiovascular outcomes associated with canagliflozin versus other non-gliflozin antidiabetic drugs: population based cohort study." BMJ 2018;360:k119 http://dx.doi.org/10.1136/bmj.k119
 
Patorno, Elisabetta et al. "Empagliflozin and the Risk of Heart Failure Hospitalization in Routine Clinical Care: A First Analysis from the Empagliflozin Comparative Effectiveness and Safety (EMPRISE) Study." Circulation. 2019 Apr 8. doi: 10.1161/CIRCULATIONAHA.118.039177


 ◦ High level of low-density lipoprotein cholesterol (LDL-C), defined as N130 mg/dL (N3.36 mmol/L) regardless of lipid-lowering therapy 	
N/A/Use the labs whenever possible
	
Patorno, Elisabetta et al. "Cardiovascular outcomes associated with canagliflozin versus other non-gliflozin antidiabetic drugs: population based cohort study." BMJ 2018;360:k119 http://dx.doi.org/10.1136/bmj.k119
 
Patorno, Elisabetta et al. "Empagliflozin and the Risk of Heart Failure Hospitalization in Routine Clinical Care: A First Analysis from the Empagliflozin Comparative Effectiveness and Safety (EMPRISE) Study." Circulation. 2019 Apr 8. doi: 10.1161/CIRCULATIONAHA.118.039177

 ◦ Low level of high-density lipoprotein cholesterol (HDL-C), defined as b40 mg/dL (b1.04 mmol/L) for men or b50 mg/dL (b1.30 mmol/L) for women 	
N/A/Use the labs whenever possible
	
Patorno, Elisabetta et al. "Cardiovascular outcomes associated with canagliflozin versus other non-gliflozin antidiabetic drugs: population based cohort study." BMJ 2018;360:k119 http://dx.doi.org/10.1136/bmj.k119
 
Patorno, Elisabetta et al. "Empagliflozin and the Risk of Heart Failure Hospitalization in Routine Clinical Care: A First Analysis from the Empagliflozin Comparative Effectiveness and Safety (EMPRISE) Study." Circulation. 2019 Apr 8. doi: 10.1161/CIRCULATIONAHA.118.039177

 * Hypertension, as confirmed at the enrolment visit ◦ BP N140/N90 mm Hg, or 	
Measured 180 days prior to drug initiation in any diagnosis position and inpatient or outpatient care setting - Hypertension ICD-9 codes 401.x – 405.x
	
Patorno, Elisabetta et al. "Cardiovascular outcomes associated with canagliflozin versus other non-gliflozin antidiabetic drugs: population based cohort study." BMJ 2018;360:k119 http://dx.doi.org/10.1136/bmj.k119
 
Patorno, Elisabetta et al. "Empagliflozin and the Risk of Heart Failure Hospitalization in Routine Clinical Care: A First Analysis from the Empagliflozin Comparative Effectiveness and Safety (EMPRISE) Study." Circulation. 2019 Apr 8. doi: 10.1161/CIRCULATIONAHA.118.039177

 ◦ BP N130/N80 mm Hg on BP-lowering agent 	
Measured as a dispensing for one of the following 180 days prior to drug initiation - Diuretics/ACE/ARB/Calcium channel blockers/Beta blockers
	

* Currently smoking, as confirmed at the enrolment visit
	
Measured 180 days prior to drug initiation in any diagnosis position and inpatient or outpatient care setting - Smoking ICD codes 305.1x 984.84 CPT codes 99406, 99407, G0436, G0437, G9016 S9453 S4995 G9276, G9458 1034F 4004F, 4001F OR dispensing of at least one nicotine or varenicline prescription
	
V15.82
 
Patorno, Elisabetta et al. "Cardiovascular outcomes associated with canagliflozin versus other non-gliflozin antidiabetic drugs: population based cohort study." BMJ 2018;360:k119 http://dx.doi.org/10.1136/bmj.k119
 
Patorno, Elisabetta et al. "Empagliflozin and the Risk of Heart Failure Hospitalization in Routine Clinical Care: A First Analysis from the Empagliflozin Comparative Effectiveness and Safety (EMPRISE) Study." Circulation. 2019 Apr 8. doi: 10.1161/CIRCULATIONAHA.118.039177
 
Desai, Rishi J et al. "Identification of smoking using Medicare data—a validation study of claims-based algorithms." Pharmacoepidemiology and drug safety vol. 25,4 (2016): 472-5. doi:10.1002/pds.3953

Appendix A

5	Women of childbearing potential must take precautions to avoid pregnancy throughout the study and for 4 weeks after intake of the last dose. Men participating in the study should also take precautions not to father a child while participating in the study and for 4 weeks after intake of the last dose.	Since this is an inclusion criteria, it's difficult to implement the contraceptive use requirement here, but we have pregnancy as an exclusion criteria later, so this requirement is implemented then.	
6	Provision of informed consent before any study specific procedures	N/A	
EXCLUSION CRITERIA			
1	Any conditions that, in the opinion of the investigator, may render the patient unable to complete the study including non-CV disease (eg, active malignancy, cardiomyopathy, cirrhosis, or chronic lung disease) with a likely fatal outcome within 5 years	Measured 180 days prior to drug initiation - CCI >= 95 percentile	Gagne, Josh J et. al. "A combined comorbidity score predicted mortality in elderly patients better than existing scores." J Clin Epidemiol. 2011 Jul;64(7):749-59. doi: 10.1016/j.jclinepi.2010.10.004. Sun, Jenny W et. al. "Validation of the Combined Comorbidity Index of Charlson and Elixhauser to Predict 30-Day Mortality Across ICD-9 and ICD-10." Med Care. 2018 Sep;56(9):812. doi: 10.1097/MLR.0000000000000954.
2	Current or previous (within 6 months) treatment with an incretin-based therapy such as DPP-4 inhibitors and/or GLP-1 mimetics	Measured 180 days prior to drug initiation - Current or previous (prior 6 months) occurrence of incretin-based mimetics. Drugs in the incretin mimetic class include exenatide, liraglutide, sitagliptin, saxagliptin, alogliptin, and linagliptin	Source- https://www.fda.gov/Drugs/DrugSafety/InformationbyDrugClass/ucm343516.htm
3	Acute vascular (cardiac or stroke) event <2 months before randomization	Measured 60 days prior to drug initiation in any diagnosis/procedure position and inpatient care setting - ACS/unstable angina 411.xx Any stroke ICD-9 Dx: 430.xx, 431.xx, 433.xx, 434.xx, 436.xx	Patorno, Elisabetta et al. "Cardiovascular outcomes associated with canagliflozin versus other non-gliflozin antidiabetic drugs: population based cohort study." BMJ 2018;360:k119 http://dx.doi.org/10.1136/bmj.k119 Patorno, Elisabetta et al. "Empagliflozin and the Risk of Heart Failure Hospitalization in Routine Clinical Care: A First Analysis from the Empagliflozin Comparative Effectiveness and Safety (EMPRISE) Study." Circulation. 2019 Apr 8. doi: 10.1161/CIRCULATIONAHA.118.039177
4	Initiation of chronic dialysis and/or renal transplant and/or a serum creatinine >6.0 mg/dL	Measured 180 days prior to drug initiation in any diagnosis position and inpatient or outpatient care setting - Kidney transplant Codes include: -ICD9 dx codes: o V42.0x, Kidney transplant status o 996.81 Complications of transplanted kidney -ICD9 prox codes: o 55.6x, Transplant of kidney (Exclude 55.61) -CPT4 codes: o 50360, Renal allotransplantation, implantation, graft, w/o donor & recipient nephrectomy o 50365, Renal allotransplantation, implantation, graft, w/ donor & recipient nephrectomy Dialysis (Please see Dialysis sheet)	Patorno, Elisabetta et al. "Cardiovascular outcomes associated with canagliflozin versus other non-gliflozin antidiabetic drugs: population based cohort study." BMJ 2018;360:k119 http://dx.doi.org/10.1136/bmj.k119 Patorno, Elisabetta et al. "Empagliflozin and the Risk of Heart Failure Hospitalization in Routine Clinical Care: A First Analysis from the Empagliflozin Comparative Effectiveness and Safety (EMPRISE) Study." Circulation. 2019 Apr 8. doi: 10.1161/CIRCULATIONAHA.118.039177
5	Pregnant or breastfeeding	Measured 180 days prior to drug initiation in any diagnosis position and inpatient or outpatient care setting- Pregnancy : Please see Pregnancy sheet.	
6	History of human immunodeficiency virus	Measured 180 days prior to drug initiation in any diagnosis/procedure position and inpatient care setting or a dispensing of one of the following drugs - HIV 042 Human immunodeficiency virus [HIV] disease 079.53 Human immunodeficiency virus, type 2 [HIV-2] V08 Asymptomatic human immunodeficiency virus [HIV] infection status OR filled prescription for HIV treatment: Please see HIV Treatment sheet .	Patorno, Elisabetta et al. "Cardiovascular outcomes associated with canagliflozin versus other non-gliflozin antidiabetic drugs: population based cohort study." BMJ 2018;360:k119 http://dx.doi.org/10.1136/bmj.k119 Patorno, Elisabetta et al. "Empagliflozin and the Risk of Heart Failure Hospitalization in Routine Clinical Care: A First Analysis from the Empagliflozin Comparative Effectiveness and Safety (EMPRISE) Study." Circulation. 2019 Apr 8. doi: 10.1161/CIRCULATIONAHA.118.039177

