5.3 Flowchart of the study cohort assembly

	Optum	Truven	Medicare

	Less Excluded Patients	Remaining Patients	Less Excluded Patients	Remaining Patients	Less Excluded Patients	Remaining Patients
All patients in the database		74,864,884		191,990,035		23,466,175
Patients who used exposure or a reference between 20 January 2010 to Dec 2017 (for Marketscan)/March 2019 (for Optum) and 01 January 2012-December 2017 for Medicare	-73,333,681	1,531,203	-189,850,391	2,139,644	-20,002,243	3,463,932
Patients who have continuous 6 months registration in the database	-198,718	1,332,485	-233,411	1,906,233	-926,605	2,537,327
Patients without prior use of reference	-837,680	494,805	-1,282,498	623,735	-1,516,234	1,021,093
Patients without prior use of exposure	-58,834	435,971	-71,555	552,180	-57,547	963,546
Excluded because patient qualified in >1 exposure category	-193	435,778	-301	551,879	-111	963,435
Patients who did not have missing age information	-13	435,765	0	551,879	0	963,435
Patients who did not have missing gender information	-26	435,739	0	551,879	0	963,435
Excluded based on Inclusion 1- DM Type 2	-20,512	415,227	-49,327	502,552	-8,942	954,493
Excluded based on Inclusion 2- Age >=40	-8,101	407,126	-17,260	485,292	0	954,493
Excluded based on Inclusion 4- High risk for a CV event defined as having either established CV disease and/or multiple risk factors	-34,138	372,988	-73,801	411,491	-3,577	950,916
Excluded based on Exclusion1- CCI >=10	-3,466	369,522	-1,659	409,832	-17,277	933,639
Excluded based on Exclusion 2- treatment with an incretin-based therapy such as DPP-4 inhibitors and/or GLP-1 mimetics	-13,198	356,324	-18,748	391,084	-33,418	900,221
Excluded based on Exclusion 3- Acute vascular (cardiac or stroke) event <2 months [i.e. ACS/unstable angina OR Any stroke (inpatient, any)]	-766	355,558	-1,546	389,538	-1,979	898,242
Excluded based on Exclusion 4- chronic dialysis or renal transplant	-592	354,966	-434	389,104	-2,718	895,524
Excluded based on Exclusion 5- Pregnancy	-7	354,959	-11	389,093	-9	895,515
Excluded based on Exclusion 6- HIV/AIDS (dx and meds) with ICD10 CODES	-129	354,830	-104	388,989	-206	895,309
Excluded based on Exclusion 7- Lupus	-174	354,656	-122	388,867	-517	894,792
Excluded based on Exclusion 8- long-term (>30 consecutive days) oral corticosteroids use	-2,286	352,370	-2,495	386,372	-7,501	887,291
Excluded based on Exclusion 9- Morbid Obesity	-3,600	348,770	-2,126	384,246	-6,087	881,204

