6.3.1 Outcome variables

Effectiveness outcomes of interest (definitions provided in **Appendix A**):

- **Primary outcome:** 3-point major adverse cardiovascular events (MACE), i.e., non-fatal myocardial infarction, non-fatal stroke, or CV mortality
- Secondary outcomes: Individual MACE components:
 - Hospital admission for MI (for purposes of this individual component, fatal MI is included)
 - Hospital admission for stroke (for purposes of this individual component, fatal stroke is included)
 - All-cause mortality/CV mortality:
 - All-cause inpatient mortality identified using discharge status codes will be used as a proxy for "CV mortality" in commercial databases
 - Information on CV mortality through data linkage with the National Death Index (NDI) will only become available at a later date for Medicare and will be used in secondary analyses.

Control outcomes of interest (control outcomes only serve to assess aspects of study validity but are not further interpreted):

1. Severe hypoglycemia (we expect to see protective effect; American Diabetes Association, 2018)

Control outcome definitions

Outcome	Hospital Discharge Code(s)	Comments
Severe hypoglycemia	Severe hypoglycemia Any-position ED or primary inpatient ICD-9 diagnosis: 251.0, 251.1x, 251.2x, or 250.8x. Outcomes identified by 250.8x are not included if they co-occur with one of the following diagnoses: 259.8, 272.7, 681.xx, 682.xx, 686.9, 707.1x, 707.2x, 707.8, 707.9, 709.3, 730.0x, 730.1x, 730.2x, 731.8	Note- The corresponding ICD-10 codes will be used also

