After review of initial feasibility and power analyses, complete creation of the remaining covariates (see Table 1 below for list of covariates). Again, using the dummy outcome of a 90-day gap in database enrollment, complete a 1:1 PS-matched analysis. The PS should include the complete list of covariates (excluding laboratory values, which are missing in some patients).

- Provide plot of PS distributions stratified by treatment group.

Note- Please refer to **Appendix B**.

- Report covariate balance after matching.

Note- For Table 1, please refer to **Appendix B**.

- Report reasons for censoring by treatment group.

	Overall	Referent	Exposure
Dummy Outcome	0 (0.00%)	0 (0.00%)	0 (0.00%)
Death	1,783 (0.98%)	1,051 (1.15%)	732 (0.80%)
Start of an additional exposure	10,211 (5.61%)	976 (1.07%)	9,235 (10.14%)
End of index exposure	122,449 (67.23%)	61,560 (67.60%)	60,889 (66.86%)
Specified date reached	11,855 (6.51%)	7,184 (7.89%)	4,671 (5.13%)
End of patient enrollment	25,411 (13.95%)	13,085 (14.37%)	12,326 (13.54%)

Switch to other SUs (for censoring) + nursing home admission	10,419 (5.72%)	7,208 (7.92%)	3,211 (3.53%)
--	----------------	---------------	---------------

- Report follow-up time by treatment group.

Patient Group	Median Follow-Up Time (Days) [IQR]		
	Optum	Marketscan	Medicare
Overall Patient Population	139 [58-344]	153 [82-367]	155 [85-373]
Referent	144 [78-354]	180 [102-432]	180 [102-432]
Exposure	132 [58-331]	140 [58-323]	140 [58-323]

- Report overall risk of the primary outcome.

	Optum	Marketscan	Medicare
Risk per 1,000 patients	13.68	16.21	38.38

10. Final Power Assessment

Date conducted: 2/1/2019

- Re-calculate power in the appropriate excel table, using the revised number of matched patients from the PS-match in Section 9. All other parameters in the table should be the same as in Section 8. If the study is to be implemented in more than one database, copy and paste excel sheet to report power for each database separately and for the pooled analysis that uses data from all databases together. Power calculations are based on the formulas from Chow et al. (2008).
 - Pooled

Non-inferiority Analysis		Superiority Analysis	
Number of patients matched		Number of patients matched	
Reference	91,063	Reference	91,063
Exposed	91,063	Exposed	91,063
Risk per 1,000 patients	22.76	Risk per 1,000 patients	22.76
Assumed HR from RCT	1	Desired HR from RCT	0.83
Alpha (2-sided)	0.05	Alpha (2-sided)	0.05
Non-inferiority margin	1.3		

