Appendix A

Mortality- Dependent on data source.

1. All-cause mortality / inpatient mortality

Identified using the vital status file-

Medicare

Identified using the discharge status codes-

Optum-

- 20 = EXPIRED
- 21 = EXPIRED TO BE DEFINED AT STATE LEVEL
- 22 = EXPIRED TO BE DEFINED AT STATE LEVEL
- 23 = EXPIRED TO BE DEFINED AT STATE LEVEL
- 24 = EXPIRED TO BE DEFINED AT STATE LEVEL
- 25 = EXPIRED TO BE DEFINED AT STATE LEVEL
- 26 = EXPIRED TO BE DEFINED AT STATE LEVEL
- 27 = EXPIRED TO BE DEFINED AT STATE LEVEL
- 28 = EXPIRED TO BE DEFINED AT STATE LEVEL
- 29 = EXPIRED TO BE DEFINED AT STATE LEVEL
- 40 = EXPIRED AT HOME (HOSPICE)
- 41 = EXPIRED IN A MEDICAL FACILITY (HOSPICE)
- 42 = EXPIRED - PLACE UNKNOWN (HOSPICE)

Truven-

- 20 - Died
- 22 - Died
- 23 - Died
- 24 - Died
- 25 - Died
- 26 - Died
- 27 - Died
- 28 - Died
- 29 - Died
- 40 - Other died status or Expired at home (Hospice claims only) (depends on year)
- 41 - Other died status or Expired in medical facility (Hospice claims only) (depends on year)

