Appendix A

- 42 - Other died status or Expired - place unknown (Hospice claims only) (depends on year)
- 21 - Died or Disch./Transf. to court/law enforcement (depends on year)

2. CV mortality

Information on CV mortality through data linkage with the National Death Index (NDI) will be available for Medicare and Optum Clininformatics at a later date. We will conduct secondary analyses using CV mortality at that time.

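### The propensity score has no malignancy covariate, although the implemented primary composite counts all-cause death

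*Protocol*

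**What the plan says.** The Protocol and the Combined protocol and SAP agree on every point used here.

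- **Trial criterion.** Appendix A, Exclusion 1, records that the trial excluded patients with "non-CV disease (eg, active malignancy, cardiomyopathy, cirrhosis, or chronic lung disease) with a likely fatal outcome within 5 years".
- **Replication of that criterion.** The same row of Appendix A gives "Measured 180 days prior to drug initiation - CCI >= 95 percentile". The flowchart in Section 5.3 labels the step "Excluded based on Exclusion1- CCI >=10". No malignancy codes appear in either place.
- **Covariates.** Section 9 says "The PS should include the complete list of covariates", leaving out laboratory values. Section 6.2 places that list in Table 1 of Appendix B. Table 1 has cardiovascular, diabetes-complication, renal, liver, lung, dementia, medication, CCI, frailty and utilisation rows. It has no cancer, malignancy or neoplasm row, before or after matching.
- **Death in the primary outcome.** Section 6.3.1 names CV mortality, then states: "All-cause inpatient mortality identified using discharge status codes will be used as a proxy for" CV mortality in the commercial databases. Appendix A implements the composite as "Inpatient mortality/MI/Stroke". For Medicare, its mortality sheet gives all-cause death "Identified using the vital status file". On cause-specific CV death, which needs a later linkage, the sheet says "We will conduct secondary analyses using CV mortality at that time".

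**The concern.** Cancer is a strong predictor of death from any cause, and cancer diagnoses sit in the same claims that supply the other covariates. Because the death component is not cause-specific, cancer deaths count as primary events. The trial criterion names four conditions. Three have a related row in Table 1 (heart failure, liver disease, COPD), and malignancy has none.

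Before matching, sulfonylurea initiators were the sicker group: pooled mean CCI 2.69 against 2.33, and 4.9% against 2.0% hospitalised in the previous 30 days. A cancer difference in the same direction is plausible but unmeasured. After matching, mean CCI is 2.33 in both arms, but balance on a summed score does not establish balance on each condition that feeds it. Any cancer difference left after matching would enter the death component of the composite, and all-cause mortality as a secondary outcome.

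**Working it through.** **1. How much the CCI step removes** (Section 5.3; exclusions divided by patients entering the step):

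- Optum: 3,466 / 372,988 = 0.93%
- MarketScan: 1,659 / 411,491 = 0.40%
- Medicare: 17,277 / 950,916 = 1.82%

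A 95th-percentile cut taken within these cohorts would remove about 5%, so the two descriptions of Exclusion 1 do not match.

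**2. Share of primary events that are deaths.** The plan's pooled event count reproduces: 182,126 patients × 22.76 / 1,000 = 4,145.19. The 22.76 is the unweighted mean of the database risks, (13.68 + 16.21 + 38.38) / 3. Summing the databases' own expected events (Section 10) gives 568.32 + 945.04 + 3,157.98 = 4,671.35, which I use here. The Section 9 censoring table has 1,051 + 732 = 1,783 deaths.

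- 1,783 / 4,671 = 0.38 (against the plan's 4,145 it is 0.43)

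This is a rough ceiling, because some deaths follow an MI or stroke that has already counted.

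**3. Illustrative bias.** Let p0 and p1 be cancer prevalence after matching in the sulfonylurea and saxagliptin arms, and m the mortality ratio for cancer. All three are assumptions; the documents give none of them.

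- Death factor = (1 + p1(m − 1)) / (1 + p0(m − 1))
- Composite factor = 1 − 0.38 × (1 − death factor)

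| p0 vs p1 | m | Death factor | Shift in mortality | Shift in composite |
|---|---|---|---|---|
| 6% vs 5.5% | 3 | 1.11/1.12 = 0.991 | 0.9% | 0.3% |
| 6% vs 5.5% | 5 | 1.22/1.24 = 0.984 | 1.6% | 0.6% |
| 10% vs 8.5% | 3 | 1.17/1.20 = 0.975 | 2.5% | 1.0% |
| 10% vs 8.5% | 5 | 1.34/1.40 = 0.957 | 4.3% | 1.6% |

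With a share of 0.43 the last figure becomes 1.8%. A harsher case (10% vs 7%, m = 6, share 0.4) gives a death factor of 1.35/1.50 = 0.90 and a composite factor of 0.96. Equal prevalence gives 1.00, and reversing the prevalences reverses the direction.

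**4. Against precision.** With equal arms, SE(log HR) ≈ 2/√events.

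- Composite: 2/√4,671 = 0.029, so a 1.6% shift is about half an SE.
- Mortality: 2/√1,783 = 0.047, so a 4.3% shift is about 0.9 SE.
- At a true HR of 1.00 the upper 95% limit is about exp(1.96 × 0.029) = 1.06, far below 1.3 with or without a shift of this size.

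**The case against.** The strongest reply is that the score already carries much general morbidity: two frailty scores, hospitalisations in several windows, hospital days, emergency visits, counts of distinct diagnoses and medications, and opioid use, nearly all with pooled standardised differences of 0.00 to 0.02 after matching. Some laboratory values, which were not in the score, also moved into balance: pooled albumin from −0.13 to 0.00 and creatinine from 0.13 to −0.03. HbA1c (0.12) and glucose (0.11) did not, and more than 80% of Optum and MarketScan patients have no value for these tests. The later CV-mortality analysis would deal with non-CV deaths directly. Appendix A plans it for Medicare and Optum, which hold 61,913 of 91,063 matched pairs (68%).

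This stands as a limit on the point. A reader might infer that cancer is controlled only through the CCI. The documents do not support that: the other covariates may absorb part of the risk, and neither the CCI's nor the frailty scores' components are listed. What the reply cannot do is show that cancer is balanced.

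Two other inferences also fail:

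- **That most cancer patients remain in the cohort.** The documents give no cancer prevalence before or after the CCI step.
- **That 1,051 against 732 deaths shows confounding the covariates missed.** These are raw counts under unequal follow-up (median 144 vs 132 days in Optum, 180 vs 140 in the other two) and unequal censoring (1.07% of referent and 10.14% of exposed patients censored for starting an additional exposure). No adjusted mortality comparison exists. The largest shift in the table, 4.3%, is also far below the crude 30% gap (732/1,051 = 0.70).

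**Conclusion.** The point holds as a gap in covariate control and in what can be checked. It is not a demonstrated bias. Malignancy is missing from the covariates, death in the implemented composite is all-cause, and the trial's malignancy exclusion has no designated stand-in beyond a CCI cut-off that is described in two different ways.

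Size and direction are unknown. Under the assumed differences of 0.5–1.5 points and mortality ratio of 3–5, mortality moves by about 0.9–4.3% and the composite by at most about 0.3–1.6%, using 38% as the ceiling on death's share. A reader might infer that the non-inferiority conclusion is at risk; the figures do not support that. No stated sample size, event count or power figure is in dispute on this point. It is a worthwhile improvement of low severity, and it matters more for the mortality outcome than for the composite.

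**What to change.** Before the Section 13 analyses:

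- Add baseline malignancy, any and metastatic, from the 180-day window to the covariate list.
- Re-estimate the score, re-match in each database, and show the new rows in Table 1.
- Reconcile the two CCI thresholds for Exclusion 1, so that the criterion applied is the one described.

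The change can still be made without sight of comparative results: the Section 9 match uses a dummy outcome, and Section 13 carries no completion date.

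The cost is one or two code lists, a rerun of the match, and refreshed balance, censoring and power tables. Those tables were reviewed on 12/9/19 and 12/20/19, so a short re-review is needed. The list would also depart slightly from the published empagliflozin cohort study on which it is based.
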